3 STUDY DESIGN

This is a 12-mo. randomized control trial in 80 non-demented adults with DS. Participants will be randomized (2:2:1) to attend 40 min. remotely delivered group MVPA sessions (Zoom™ Video Conferencing Inc., San Jose, CA) at a low frequency (1 session/wk., RL) or high frequency (3 sessions/wk., RH), or a usual care control (UC). In addition to the group MVPA sessions, participants in both the RL and RH arms will receive a step counter (Charge 3™, Fitbit, San Francisco, CA), access to resources for increasing MVPA, and one 20-min remotely delivered (Zoom™) individual support/education session/wk. Content for both the RL and RH arms will be identical with the exception of group MVPA session frequency (1 vs. 3/wk.). Participants in the UC arm will receive a step counter (Charge 3™, Fitbit, San Francisco, CA), access to resources for increasing MVPA, and monthly remote (Zoom™) individual support/education. The primary outcomes, daily MVPA will be assessed by portable accelerometer (ActiGraph wGT3XBT, ActiGraph LLC, Pensacola, FL) at baseline, 3, 6, 9 and 12 mos. The secondary outcomes, cardiovascular fitness, quality of life, cognitive function and brain parameters related to AD (whole and regional brain volume, functional connectivity, cerebral blood flow) will be assessed at baseline, 6, and 12 mos. With the exception of assessment of daily MVPA by accelerometer, all outcomes will be assessed at the University of Kansas Medical Center, in Kansas City, KS. The exercise intervention will take place in the participants home.

| Table 1: Design Overview | | | |
|--|-------------------------------|------------------------------|------------------------------|
| | Intervention Arms | | |
| | Remote High (n=32) | Remote Low (n=32) | Usual Care (n=16) |
| MVPA recommendation | 150 min/wk. | 150 min/wk. | 150 min/wk. |
| Group MVPA sessions | Yes | Yes | No |
| Delivery format | Zoom™ video conferencing | Zoom™ video conferencing | NA |
| Frequency | 3d/wk. | 1d/wk. | NA |
| Intensity | ≥ 3 METS | ≥ 3 METS | NA |
| Duration | 40 min | 40 min | NA |
| Content | Stretch/aerobic activity/RE | Stretch/aerobic activity/RE | NA |
| Access to PA resources | Yes | Yes | Yes |
| MVPA Self-monitoring | Fitbit | Fitbit | Fitbit |
| Education/support/feedback sessions | Yes | Yes | Yes |
| Participants | DS adult + Study Partner | DS adult + Study Partner | DS adult + Study Partner |
| Frequency | 2x/mo | 2x/mo | 2x/mo |
| Delivery format | Zoom™ | Zoom™ | Zoom™ |

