Group MVPA session-content. Each session will include a warm-up (~5 min), moderate-to-vigorous intensity aerobic and resistance exercise (~30 min.), and cool-down/stretching (~5 min.). Resistance exercise may be especially relevant, as adults with DS have reduced muscle strength compared with their typically developing peers ³. The aerobic/resistance exercises, accompanied by music, will include walking/jogging in place, dancing, imitating animal movements, vertical/horizontal jumps, squats, and Thera-Band exercises for major muscle groups. Activities will be modified for participants having difficulty with specific movements. The intensity of the initial sessions, as determined by Fitbit, will be light-to-moderate, with intensity increasing to moderate-to-vigorous at ~ 6 wks. All participants will be able to see, hear, and speak to each other during the group sessions. During each session, health educators will encourage interactions between participants in

support of their peer's efforts to increase MVPA and provide participant feedback relative to their level of weekly MVPA as assessed by the Fitbit. As the intervention progresses, participants will be asked to volunteer to create and lead the group in a brief (3-5 min) exercise bout. Participants will also be encouraged to interact with each other by providing verbal support to each other ("great job", "keep it up"), performing activities such as tossing an imaginary ball to other participants, or challenging other participants to complete a skill such as 10 hops on one leg etc. All group sessions will be video recorded.

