Quality of Life. Quality of life will be assessed at baseline, 6, and 12 mos. with the Personal Well-Being Index-Intellectual Disability(PWI-ID)^{62, 63}. This instrument contains 7 items, each corresponding to a quality of life domain: standard of living, health, life achievement, personal relationships, personal safety, community-connectedness, and future security. Cronbach alpha of 0.76, and 1- to 2-wk. test-retest reliability of 0.58 have been reported in adults with IDD⁶². The PWI-ID scale differs from the original Personal Well-Being Index (PWI-A) in that it incorporates a pre-testing protocol to determine whether, and to what level of complexity, respondents are able to use the scale. The ID version also uses more simple and concrete wording. An additional question which asks how happy or sad the respondent is with life as a whole is included. A reduced choice format, illustrated as a series of outline faces, from very sad to happy, is provided to enhance comprehension and substitutes for the Likert scale used in the PWI-A version⁶³.

Neuroimaging (Sub-sample).. Neuroimaging measures of brain volume i.e. structural MRI, functional connectivity, i.e. resting state MRI (rsMRI), blood flow, i.e. arterial spin labeling (ASL), and spectroscopy (MRS) will be assessed at baseline, 6, and 12 mos. utilizing the scan parameters currently implemented by the NIAD and ABC-DS Structural MRI imaging has elucidated the specific brain regions impacted by dementia in DS. These grey matter changes are detectable prior to the development of signs of clinical dementia^{64, 65} and have been impacted by cardiovascular fitness/MVPA⁵⁶. Structural MRI is a feasible test in adults with DS. In a recent review of 9 trials that used rsMRI in adults with DS⁶⁶, 4 reported no scanning issues, and in the remaining 5, ~17% of participants were excluded due to motion artifact with those who have more severe intellectual

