8.3 Data Analyses

Our primary aim is to assess daily MVPA (min.) among the RL, RH, and UC arms at baseline, 3, 6, 9, and 12 mos. and obtain effect sizes for change in MVPA over 12-mos. We will calculate the mean and standard deviation and 95% confidence intervals of daily MVPA at each time point for all 3 groups, as well as for the change from baseline to each time point. This descriptive information will be summarized graphically which will aid in determining if, and when, differences in MVPA arise among and across the 3 groups. The corresponding effect sizes at each time point will be calculated as the differences in the mean divided by the common standard deviation. We will also estimate the correlation of MVPA over time within individuals. This information will be critical to identifying whether single point in time or longitudinal assessments will be utilized to identify the sample size needed for future large-scale confirmatory trials. We will subsequently run a repeated measures ANOVA comparing the change in baseline at each time point across the three groups using a linear mixed model approach with an autoregressive correlation structure over time. The model will include a main effect of group and time and a group by time interaction which will provide an estimate of the treatment effect when modeling longitudinally. The data from this trial will provide solid preliminary data to determine the potential for an effect and inform the best design to employ in subsequent trials.

Our first secondary aim will assess the impact of MVPA across the RL, RH, and UC arms on cardiovascular fitness, quality of life, cognitive function, and brain parameters (whole and regional brain volume, functional connectivity, cerebral blood flow) at baseline, 6, and 12 mos. We will estimate the correlation of change in MVPA on changes in cardiovascular fitness, quality of life, cognitive function, whole and regional brain volume, functional connectivity and cerebral blood flow at 6 and 12 mos. This analysis will be completed with the total sample, irrespective of study arm. Thus 80 participants will provide at least 80% power to detect correlation of 0.31 or higher or -0.31 or lower with a type I error rate of 5%. Sixty subjects (25% loss to follow-up) will still allow us to detect a correlation of 0.36 or higher or -0.36 or lower with 80% power and type I error rate of 5%.

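### The pooled correlation for secondary aim 1 ignores arm, so an effect of live group contact could appear as an association with MVPA

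*Combined protocol and SAP*

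**What the plan says.** Section 8.3 states the aim in causal terms: "Our first secondary aim will assess the impact of MVPA across the RL, RH, and UC arms on cardiovascular fitness, quality of life, cognitive function", together with brain measures. The only analysis given for it is this: "We will estimate the correlation of change in MVPA on changes in cardiovascular fitness, quality of life, cognitive function" and the imaging measures, at 6 and 12 months. On the sample, it says: "This analysis will be completed with the total sample, irrespective of study arm". Power follows from that choice: "80 participants will provide at least 80% power to detect correlation of 0.31 or higher or -0.31 or lower", and "Sixty subjects (25% loss to follow-up) will still allow us to detect a correlation of 0.36 or higher or -0.36 or lower". No term for arm, attendance or contact is mentioned. The end of Section 8.3 adds only an exploration of demographic characteristics.

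Section 5 schedules group sessions three times a week in RH and once a week in RL; UC has none. The sessions are social by design. Participants see and talk to one another, "health educators will encourage interactions between participants in" support of each other's efforts, and members take turns leading the group. The quality-of-life scale in Section 5 has seven domains, among them "personal relationships, personal safety, community-connectedness, and future security". Section 5 describes the individual education sessions as the same in all three arms, which leaves the group sessions as the main planned difference in contact.

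**The concern.** A correlation of change scores across all participants does not compare randomised groups, so randomisation does not protect it. Arm sits behind both variables. It is intended to change MVPA, and it sets the dose of live peer contact. If contact by itself lifts an outcome, RH participants will tend to be high on both axes and UC participants low on both. The pooled correlation is then positive even when MVPA does nothing.

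The pathway is concrete for quality of life, because the scale asks directly about relationships and community connection. It is possible for cognition. The documents suggest no such route for treadmill fitness, brain volume or blood flow.

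Sections 2.1 and 8.1.1 say this trial is to inform a later one on cognition and brain health. Whether gains follow activity or group contact bears on the rationale for that trial and on its choice of control.

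**Working it through.** **The plan's own figures.** Fisher z, two-sided 5%: power = Φ(atanh(r)·√(n−3) − 1.96).
- n=80, r=0.31: 80.3%; smallest detectable |r| at 80% power is 0.309.
- n=60, r=0.36: 81.2%; smallest detectable |r| is 0.355.

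Both stated figures are reproduced.

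**Inputs for the confounding check.**
- Allocation 32:32:16 (Section 8.1), so weights are 0.4, 0.4 and 0.2.
- Group sessions over 52 weeks (Section 6.2.5): up to 3×52 = 156 in RH, 1×52 = 52 in RL, 0 in UC.
- MVPA available from those sessions (Section 5, Homework assignments): 90 and 30 min/wk, i.e. 90/7 = 12.9 and 30/7 = 4.3 min/day, and 0 in UC. Using these as the arm shifts assumes full attendance and no other difference in MVPA change.
- Within-arm SD of MVPA change: 10 min/day, assumed. Section 8.1 gives about 10 for daily MVPA at 12 months, not for change. The two agree if the within-person correlation is 0.5, because 10·√(2(1−0.5)) = 10.
- Contact effect: d outcome SDs in RH, d/3 in RL, 0 in UC. This is an assumption, with d from 0.3 to 0.8.
- No association between MVPA change and outcome change within arms.

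**Induced correlation.** The between-arm variance of MVPA change is 26.4. The between-arm covariance with the outcome is 2.06d, and the between-arm variance of the outcome is 0.16d². So

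r = 2.06d / √[(100 + 26.4)(1 + 0.16d²)].

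Rejection rates of the zero-correlation test (Fisher z, n−3):

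| d | r, full shift | n=80 | n=60 | n=80, half the MVPA shift |
|---|---|---|---|---|
| 0.3 | 0.05 | 8% | 7% | 6% |
| 0.5 | 0.09 | 12% | 10% | 7% |
| 0.8 | 0.14 | 23% | 19% | 10% |

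Simulation with 20,000 runs agrees: 7.7%, 12.3% and 23.7% at n=80 with the full shift.

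**Sensitivity, n=80.**
- d=0.5, SD 8 to 12: 15% to 10%.
- SD 7, d=0.8: r=0.18, rejection 36.8%.
- Contact equally effective in RH and RL, SD 10: 8% at d=0.5 and 13% at d=0.8.
- SD 14, half the shift, equal contact effect, d=0.3: r=0.01, rejection 5.1%.
- d=0: no bias from this source.

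With arm in the model, the simulated rejection rate at n=80 stays at 4.9% throughout. That is because contact is constant within each arm in this model.

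**Price of adjusting for arm.** Two arm indicators replace n−3 by n−5. If the correlation itself did not change, power would be 79.3% (0.31, n=80) and 79.8% (0.36, n=60), and the detectable within-arm |r| would be 0.313 and 0.361. But adjustment also removes the between-arm spread in MVPA, which here is 26.4/126.4 = 21% of its variance. With the MVPA slope and residual SD held fixed, r²/(1−r²) shrinks by the factor 100/126.4:
- r=0.31: 0.0961/0.9039 = 0.1063, which becomes 0.0841. Within-arm r = √(0.0841/1.0841) = 0.279, power 69.8% at n=80.
- r=0.36: 0.1296/0.8704 = 0.1489, which becomes 0.1178. Within-arm r = √(0.1178/1.1178) = 0.325, power 70.5% at n=60.

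The loss is therefore about 10 percentage points on these inputs, rather than 1.

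**The case against.** The case for leaving the plan alone has real force.

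- **The size is assumed.** No contact effect is given anywhere. All arms share the weekly MVPA target and the Fitbit, and RL is asked to make up its shortfall outside sessions, so the arm shifts may be smaller than those used. With half the shift the rejection rate is only 6% to 10%. This stands. The induced correlations are modest and well below the 0.31 that the plan is powered for.
- **The test size is right.** A reader might infer that the stated 5% error rate is wrong. It is not. The null hypothesis is zero correlation, and if contact induces a correlation, rejecting that null is correct. What fails is the step from rejection to an MVPA effect.
- **Adjustment does not isolate MVPA.** A reader might infer that an arm term settles attribution. It removes only the between-arm part. Within RH and RL, those who attend more receive both more MVPA and more contact. The adjusted estimate also gives up the randomised part of the MVPA variation.
- **The programme may be the target.** The later trial would use the video-conference approach, so an association with the whole package is of interest. That supports keeping the pooled figure, but not describing it as the effect of MVPA.

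The plan does say that it will estimate a correlation, and a causal report is not certain. The aim is nevertheless worded causally, and nothing else in Section 8.3 limits the interpretation.

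**Conclusion.** The concern holds as a matter of interpretation and reporting. The pooled correlation cannot separate MVPA from group contact, because both rise together by arm. Under the assumptions above, the false lead is an r of 0.05 to 0.14, with zero correlation rejected in 8% to 23% of trials at n=80 and 7% to 19% at n=60. It is smaller if the arms differ less in MVPA, and absent if contact has no effect.

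It would go too far to say that a positive result would be an artefact, or that every outcome in the aim is exposed. The documents support neither: they give no contact effect, and the route is credible mainly for quality of life and, less clearly, cognition.

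One related inconsistency needs reconciling. The text of Section 3 gives weekly individual sessions for RL and RH and monthly sessions for UC, whereas its Table 1 and Section 5 give two a month in every arm. If individual contact also differed by arm, the confounding could be larger.

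**What to change.** In Section 8.3:

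1. Keep the pooled correlation and its stated power, but describe it as an association that may reflect the programme as a whole.
2. Report beside it the arm-adjusted estimate, from a regression of outcome change on MVPA change plus arm.
3. State how the two will be read. An association seen only in the pooled analysis is not attributed to MVPA. One that persists within arms is supportive but not proof.
4. Examine recorded session attendance (Sections 5 and 5.1) as a further check within RH and RL.

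The cost is a few sentences and one model term, with no new data. The price is precision. If arm explains about 21% of the variance of MVPA change, a pooled r of 0.31 or 0.36 corresponds to about 0.28 or 0.32 within arms, with about 70% power. The adjusted result should therefore be labelled a supporting estimate, and a non-significant one should not be read as evidence against MVPA.

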1.2 Secondary Objectives

Secondary aim 1: Assess the impact of MVPA across the RL, RH, and UC arms on cardiovascular fitness, quality of life, cognitive function and brain parameters related to AD (whole and regional brain volume, functional connectivity, cerebral blood flow) at baseline, 6, and 12 mos.

Secondary Aim 2: Determine the feasibility (retention, session attendance, use of recorded sessions (RH/RL only) and safety of RL, RH, and UC arms.

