2 BACKGROUND AND RATIONALE

2.1 Background on Condition, Disease, or Other Primary Study Focus

Nearly all individuals with Down Syndrome (DS) will develop Alzheimer's Disease (AD), some beginning as early as age 30. To date, trials have failed to identify any drug that is safe or effective for the prevention of AD in adults with DS, and there is a lack of non-pharmacologic strategies for the prevention of AD in adults with DS. Previous research in typically developing adults suggests that increased MVPA may improve cognitive function and protect against age-related functional and structural brain changes; however, the potential impact of increased MVPA on the development of AD in adults with DS has not been evaluated. Despite the potential positive impact of MVPA, participation in MVPA among adults with DS is low. The limited research evaluating intervention strategies for increasing MVPA in adults with DS is not specific to adults with DS, i.e., includes all IDDs, and has been unsuccessful in increasing short-term (≤ 12 wks.) or long-term MVPA (12 mos.). Results from our 12-wk. pilot trial of a remote method which delivers real-time MVPA, led by a trained health educator, to groups of adults with DS in their homes (n=27), via video conferencing on a tablet computer demonstrated high attendance, increased MVPA during group sessions, and improvements in cognitive function. However, the sustainability, impact on total daily MVPA, optimal session frequency, and potential impacts on cognitive function and measures of brain health of remotely delivered group MVPA sessions in adults with DS are unknown.

Therefore, we will conduct a 12 mo. early stage clinical trial in 80 non-demented adults with DS to determine the feasibility and potential efficacy of remotely delivered group MVPA, delivered at two different frequencies to increase daily MVPA, relative to a usual care control. This early stage clinical trial will inform and advance the design of a subsequent late stage clinical trial while providing important data regarding the effect of MVPA on cognition and measures of brain health related to development of AD in adults with DS.

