8.1.1 Treatment Assignment Procedures

Cohorts of ~10-20 participants will be recruited and computer randomized. Participants will be stratified by sex and age (18-30 or >30) and then sequentially randomized by the study statistician with 2:2:1 allocation to the RL, RH, and UC arms.

This randomization scheme was selected to include more participants in the group video conferencing arms which, if successful, will be included in a later stage trial examining the effectiveness of increased MVPA using the video conferencing approach on cognitive function and brain health in adults with DS.

Intervention assignments will be concealed in envelopes and delivered to the study coordinator. Participant randomization will be stored on the study Redcap Database.

The study team and the participants will not be blinded to group assignment.

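### Secondary Aim 1 is analysed only by a correlation pooled over arms, so no between-arm estimate is pre-specified for fitness, quality of life, cognition or brain outcomes

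*Combined protocol and SAP*

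**What the plan says.** Section 1.2 words the aim as "Assess the impact of MVPA across the RL, RH, and UC arms on cardiovascular fitness, quality of life, cognitive function", continuing with brain parameters, at baseline, 6 and 12 months. The Précis has the same wording, and section 8.3 repeats it: "Our first secondary aim will assess the impact of MVPA across the RL, RH, and UC arms on cardiovascular fitness, quality of life, cognitive function".

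The analysis that follows in 8.3 is: "We will estimate the correlation of change in MVPA on changes in cardiovascular fitness, quality of life, cognitive function", continuing with the imaging measures, at 6 and 12 months. The analysis set comes next: "This analysis will be completed with the total sample, irrespective of study arm". Power is stated for that correlation: "Thus 80 participants will provide at least 80% power to detect correlation of 0.31 or higher or -0.31 or lower", and after dropout, "Sixty subjects (25% loss to follow-up) will still allow us to detect a correlation of 0.36 or higher or -0.36 or lower".

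Participants are "sequentially randomized by the study statistician with 2:2:1 allocation to the RL, RH, and UC arms" (8.1.1), giving 32 RH, 32 RL and 16 UC (8.1). Sections 5 and 8.1.1 explain that the ratio favours the video-conferencing arms because, if successful, they will go into a later trial of cognitive function and brain health. Section 2.1 describes this trial as "providing important data regarding the effect of MVPA on cognition and measures of brain health related to development of AD in adults with DS".

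**The concern.** The trial randomises, and it collects every Aim 1 outcome at baseline, 6 and 12 months. For these outcomes, however, arm enters no planned analysis. Three things follow.

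- **Interpretation.** A change-change correlation in the pooled sample is not protected by randomisation, yet the aim calls it impact. Section 5 describes RH and RL sessions in which participants see, hear and encourage one another; UC has no group sessions. If that contact affects quality of life or cognition, part of its effect can surface in the pooled correlation, because the arms are also designed to differ in MVPA.
- **Planning.** The later trial will need arm differences on cognition and brain measures. The plan produces arm differences for MVPA but for none of those endpoints.
- **Pre-specification.** Any by-arm results reported for these outcomes would be chosen without a written plan, possibly after the data had been seen.

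**Working it through.** **1. Does any other text supply an arm comparison?**

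| Text | Outcomes covered | Arm in the analysis? |
|---|---|---|
| 8.3, primary aim | Daily MVPA | Yes: means, intervals, effect sizes, and a mixed model with group, time and their interaction |
| 8.3, first secondary aim | Fitness, quality of life, cognition, brain measures | No: pooled correlation |
| 8.3, second secondary aim | Feasibility and safety | Yes: proportions by arm |
| 8.3, closing sentence on all analyses | All | No: demographic characteristics only |

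None does so for the Aim 1 outcomes.

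**2. The plan's own power.** Inputs from 8.3: n = 80 with r = 0.31, n = 60 with r = 0.36, type I error 5%. It is taken as two-sided because both signs of r are stated. Fisher z: power = Φ(atanh(r)·√(n−3) − 1.96).

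- n = 80: 0.3205 × 8.775 = 2.813; Φ(0.853) = 0.803.
- n = 60: 0.3769 × 7.550 = 2.845; Φ(0.885) = 0.812.

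Both figures reproduce. They are the power of the pooled correlation and of nothing else.

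**3. Precision of the arm differences that are not planned.** Arm sizes are 32, 32 and 16 from 8.1, and 24, 24 and 12 after the plan's 25% loss. The 95% half-width in outcome SD units, without baseline adjustment, is t(0.975; n1+n2−2)·√(1/n1 + 1/n2).

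| Contrast | n | Calculation | Half-width |
|---|---|---|---|
| RH or RL vs UC | 32 v 16 | 2.013 × 0.306 | 0.62 SD |
| RH vs RL | 32 v 32 | 1.999 × 0.250 | 0.50 SD |
| RH or RL vs UC, 25% loss | 24 v 12 | 2.032 × 0.354 | 0.72 SD |
| RH vs RL, 25% loss | 24 v 24 | 2.013 × 0.289 | 0.58 SD |

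Imaging is a sub-sample of unstated size (section 5, Assessments), so its intervals would be wider. Unless the sub-sample is nearly everyone, the n = 80 and n = 60 power statements do not apply to it either. With assumed sizes of 40, 30 or 20, the r detectable with 80% power is 0.43, 0.49 or 0.59.

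**4. Can the pooled correlation pick up an arm effect that does not run through MVPA?** This is an illustration on assumptions. The documents give no between-arm MVPA difference, no correlation over time and no size for any contact effect.

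- Assume that the arms differ in MVPA change by the scheduled session minutes in section 5 (90, 30 and 0 min/wk, or 12.9, 4.3 and 0 min/day).
- The SD is 10 min (8.1). With an assumed correlation of 0.5 over time, the SD of change is 10·√(2 × 0.5) = 10, so the shifts are 1.29, 0.43 and 0 SD.
- Assume no within-arm relation between MVPA and outcome.
- Let RH gain 0.5 SD on the outcome by another route, and RL a third of that.

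With arm weights 0.4, 0.4 and 0.2, the between-arm covariance is 0.103 and the total variances are 1.264 and 1.040. Pooled r = 0.103/√(1.264 × 1.040) = 0.09.

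| Non-MVPA gain in RH | RL gain | Mean pooled r | Significant at 5% |
|---|---|---|---|
| 0.5 SD | one third of RH | 0.09 | 12% |
| 0.8 SD | one third of RH | 0.14 | 23–24% |
| 0.5 SD | same as RH | 0.06 | 8% |
| 0.8 SD | same as RH | 0.09 | 13% |

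Simulation agrees with the last column, and removing arm means brings the rate back to about 5%. If the arms differ by only half the assumed MVPA, the rates fall to roughly 6% to 10%.

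**The case against.** The strongest reply is that the aim names MVPA as the exposure. "Across the arms" can mean pooled over them, and the explicit statement that arm is disregarded suggests a deliberate choice. On that reading the analysis fits the aim. This stands as a reading of the wording, so a flat contradiction between aim and analysis cannot be claimed. It does not make the correlation a randomised comparison, and it does not supply an arm estimate for the later trial.

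Three stronger inferences are tempting, and the documents do not support them.

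- **That randomisation is thrown away or the arms are never compared.** The primary MVPA analysis compares them fully, and nothing forbids by-arm reporting of the secondary outcomes. The accurate statement is that no such comparison is pre-specified.
- **That the 80% power is wrong or inflated.** It reproduces. An arm comparison on these outcomes would have much lower power, but the plan claims none for it, so the gap between the two is not an error.
- **That any benefit of group contact will be credited to MVPA.** The illustration gives a mean pooled r of only 0.06 to 0.14, under arm effects that the documents do not provide. All three arms share the 150 min/wk target, so activity outside sessions could narrow the MVPA difference and weaken the mechanism further.

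It is also fair to say that this is an early-stage trial with 16 UC participants, which gives a plausible reason for pooling. But the primary aim is itself about estimation, so low power is no reason to leave out estimates with intervals.

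**Conclusion.** The point holds in limited form. As written, Secondary Aim 1 yields one non-randomised association per outcome and visit, described as impact, and no pre-specified between-arm estimate for fitness, quality of life, cognition or brain measures. This rests on the text alone and needs no numerical assumption. The primary analysis is unaffected and the stated correlation power is correct.

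The arm differences that could be reported would be imprecise, with half-widths of about 0.5 to 0.6 SD at full enrolment and 0.6 to 0.7 SD after 25% loss. Those figures rest on the planned arm sizes, a common SD and no baseline adjustment. The mis-crediting rates (about 6% to 24% against a nominal 5%) show only that the pooled correlation can reflect more than MVPA; their size depends wholly on assumed effects. The plan should be amended, but the gap does not threaten the trial's main result.

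**What to change.** In section 8.3, under the first secondary aim:

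- (a) Keep the pooled correlation, describe it as an association, and report it beside a version adjusted for arm.
- (b) For each Aim 1 outcome, report change by arm and the RH−UC, RL−UC and RH−RL differences at 6 and 12 months, with 95% confidence intervals and effect sizes. Take them from an arm-by-visit mixed model like the one planned for MVPA, with the baseline value of the outcome as a covariate. Label them exploratory estimates, not powered tests. By-arm change with intervals and effect sizes, as already planned for MVPA, is the minimum that would close the gap.
- (c) State that the 80% power applies only to the pooled correlation. Give the unadjusted half-widths: 0.62 SD (RH or RL vs UC) and 0.50 SD (RH vs RL) with 80 participants, 0.72 and 0.58 SD with 60, and wider for the imaging sub-sample.

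The cost is a few sentences and one extra model per outcome on data already being collected, with no new participants or visits. The downside is a set of wide intervals, which readers must be told not to treat as tests.
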